## **3 PAIN AND MBS AT 3 HOURS POST DOSE**

### **3.1 Pain Freedom at 3 Hours Post Dose**

The between group difference in the percentage of subjects with pain freedom at 3 hours post-dose was assessed by computing the “risk difference” between treatment groups. This was evaluated by computing the common risk difference, using CMH weights (sample size weights), stratified by the use of prophylactic migraine medication (yes or no). The risk difference was tested at a two-sided alpha level of 0.05. Missing data at 2 hours post-dose were imputed as failures (NC=F).

Results presented for this analysis included the following:

- Common risk difference with sample size, p-value, ASE, and 95% asymptotic CIs.
- Risk difference within each strata with sample size, p-value, ASE, and 95% asymptotic CIs.
- A plot of the risk differences within each strata, and common risk difference (similar to the risk difference plot produced by SAS Proc Freq).
- Common risk for each treatment with sample size, ASE, and 95% asymptotic CIs.

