### 5.7.3.1 Pain Freedom at 2 Hours Post-Dose

Pain freedom is assessed using the number of mITT subjects that report pain levels of “none” at 2 hours post-dose on a 4-point Likert scale (0=none, 1=mild, 2=moderate, 3=severe). The information from the 4-point scale is directly summarized as follows:

- A table showing descriptive statistics for the observed data, which includes the number and percentage of subjects reporting each of the 4 pain levels at 2 hours post-dose, and the percentage of subjects with missing data, for each treatment group. The table will include exact (Clopper-Pearson) 95% CIs for each percentage.
  - This table will be repeated for Asian subjects only.

The estimand for the primary analysis is the percentage of pain free subjects. In statistical terms, this percentage is arrived at by estimating the probability or the “risk” that a subject is pain free.

The population summary, the between group difference in the percentage of pain free subjects is assessed by computing the “risk difference” between treatment groups. This is evaluated by computing the common risk difference, using Cochran-Mantel-Haenszel (CMH) weights (sample size weights), stratified by the use of prophylactic migraine medication (yes or no). The risk difference is tested at a two-sided alpha level of 0.05. Missing data at 2 hours post-dose will be imputed as failures (NC=F). If a stratum (prophylactic medication use: yes or no) has sparse data (less than 5 subjects), then the strata will be pooled.

Results presented for the primary analysis include the following:

- The number and percentage of subjects who are pain free, and those not pain free, at 2 hours post-dose. These are presented by stratum and treatment group, with asymptotic standard errors (ASE), and 95% asymptotic CIs.
- Common risk difference with sample size, p-value, asymptotic standard error (ASE), and 95% asymptotic CIs.
- Risk difference within each strata with sample size, p-value, asymptotic standard error (ASE), and 95% asymptotic CIs.
- A plot of the risk differences within each strata, and common risk difference (similar to the risk difference plot produced by SAS Proc Freq).
- Common risk for each treatment with sample size, ASE, and 95% asymptotic CIs.

The primary analysis will be repeated for the subgroups described in Section 5.2.6.

Sensitivity analyses will be conducted as follows:

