### **3.2 Freedom from MBS at 3 Hours Post Dose**

The estimand, difference in percentage of subjects with freedom from MBS at 3 hours between treatment groups was evaluated by computing the common risk difference using CMH weights (sample size weights), stratified by the use of prophylactic migraine medication (yes or no). The risk difference was tested at a two-sided alpha level of 0.05. Missing data at 3 hours post-dose was imputed as failure (NC=F). Also the use of rescue medication prior to providing data at the 3 hour assessment, taking IP prior to reporting the MBS, or failure to report a MBS are events that were imputed as treatment failures.

Results presented for this analysis included the following:

- Common risk difference with sample size, p-value, ASE, and 95% asymptotic CIs.
- Risk difference within each strata with sample size, p-value, ASE, and 95% asymptotic CIs.
- A plot of the risk differences within each strata, and common risk difference (similar to the risk difference plot produced by SAS Proc Freq).

- Common risk for each treatment with sample size, ASE, and 95% asymptotic CIs.

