## **4 OTHER ENDPOINTS AT 3 HOURS POST DOSE**

### **4.1 Freedom from Photophobia, Phonophobia, or Nausea at 3 Hours**

Freedom from photophobia, phonophobia, and nausea were assessed, by treatment group, by tabulating the number of mITT subjects who reported the presence of the symptom at migraine onset, and later reported the absence of the symptom at 3 hours post-dose. Subjects who reported the symptom at baseline, but have missing data at 3 hours post-dose were imputed as failures (NC=F). Also, subjects in the analysis set who took rescue medications on or before providing their 3 hour post-dose data were imputed as failures.

The principal measurement for the associated symptoms (phonophobia, photophobia, and nausea) is made on a binary scale (0 = absent; 1 = present). An exploratory measurement of these symptoms was also made on a 4-point Likert scale (0=none, 1=mild, 2=moderate, 3=severe).

For these three endpoints, the difference between treatment groups, was evaluated by computing the common risk difference using CMH weights (sample size weights), stratified by the use of prophylactic migraine medication (yes or no). The risk difference was tested at a two-sided alpha level of 0.05.

Results presented for these analyses included the following:

- Common risk difference with sample size, p-value, ASE, and 95% asymptotic CIs.
- Risk difference within each strata with sample size, p-value, ASE, and 95% asymptotic CIs.
- A plot of the risk differences within each strata, and common risk difference (similar to the risk difference plot produced by SAS Proc Freq).
- Common risk for each treatment with sample size, ASE, and 95% asymptotic CIs.

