### **4.2 Pain Relief at 3 Hours Post Dose**

Pain relief at 3 hours post-dose was assessed by tabulating the number of mITT subjects that reported a pain level of none or mild (responses of 0 or 1 on the 4-point Likert scale) at 3 hours post-dose by treatment group. Subjects with missing data at 3 hours post-dose were imputed as failures (NC=F). Also, subjects in the analysis set who took rescue medications on or before providing their 3 hour post-dose data were imputed as failures.

Results presented for this analysis included the following:

- Common risk difference with sample size, p-value, ASE, and 95% asymptotic CIs.
- Risk difference within each strata with sample size, p-value, ASE, and 95% asymptotic CIs.

- A plot of the risk differences within each strata, and common risk difference (similar to the risk difference plot produced by SAS Proc Freq).
- Common risk for each treatment with sample size, ASE, and 95% asymptotic CIs.

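### SAP Appendix 4, Section 3.1 ties the missing-data rule for pain freedom at 3 hours to the 2-hour entry

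*SAP*

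**What the plan says.** SAP Appendix 4, Section 3.1 sets the endpoint at 3 hours. Its opening sentence begins "The between group difference in the percentage of subjects with pain freedom at 3 hours post-dose was assessed by computing the", and the quantity computed is a risk difference with CMH weights, stratified by prophylactic medication. It adds that "The risk difference was tested at a two-sided alpha level of 0.05". The missing-data rule that follows is "Missing data at 2 hours post-dose were imputed as failures (NC=F". The section has no sentence on rescue medication.

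The neighbouring 3-hour analyses use the 3-hour time point:

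- Section 3.2 (MBS): "Missing data at 3 hours post-dose was imputed as failure (NC=F". The events counted as failure in that section include rescue, worded as "Also the use of rescue medication prior to providing data at the 3 hour assessment".
- Section 4.1 (photophobia, phonophobia, nausea): "Subjects who reported the symptom at baseline, but have missing data at 3 hours post-dose were imputed as failures (NC=F", with a rescue sentence.
- Section 4.2 (pain relief): missing 3-hour values count as failure, and the rescue rule is given as "Also, subjects in the analysis set who took rescue medications on or before providing their 3 hour post-dose data were imputed as failures".
- Section 4.3 (functional disability): neither rule is stated.

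Three general rules in the body of the SAP also bear on this. Section 2.3 defines NC=F as failure when data for the endpoint are missing, and RM=F as failure when rescue is taken at or before the event of interest. Section 5.7.1 makes rescue users failures for every efficacy evaluation that coincides with or follows the rescue.

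**The concern.** A 2-hour value is not part of the data for a 3-hour endpoint. Under the sentence as written, a recorded 3-hour success is overturned because an earlier entry is absent, and the sentence names the wrong time point for deciding whether the endpoint itself is missing.

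Isolated missed entries are to be expected here. The SAP tolerates one missed time point in the durability endpoints (Section 2.3), tabulates missing pain data at each time point from 2 to 48 hours (Section 5.6), and plans sensitivity analyses around an eDiary software fix (Section 5.7.3.1).

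At stake is whether the 3-hour pain-freedom result can be read beside the other 3-hour results and the 3-to-24-hour durability result. The primary analysis and the ordered secondary tests are not touched.

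**Working it through.** **Nearest design figure.** The plan states no figure for the 3-hour analysis. The closest is more than 95% power for 2-hour pain freedom with 550 per group (Protocol 9.2, SAP 5.1). With the Phase 2b rates of 31.4% and 15.3% (Protocol 1.3.2.8) the pooled rate is 0.2335.

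- Null SE = sqrt(2 x 0.2335 x 0.7665 / 550) = 0.0255.
- Alternative SE = sqrt((0.314 x 0.686 + 0.153 x 0.847) / 550) = 0.0250.
- z = (0.161 - 1.96 x 0.0255) / 0.0250 = about 4.4, so power exceeds 99.99%.

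The stated power is reproduced, but it does not bear on the 3-hour rule. That has to be settled from the text.

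**Test subjects.** Take three mITT subjects.

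- A: no 2-hour entry; no pain at 3, 4, 6, 8 and 24 hours; no rescue.
- B: 2-hour entry present, 3-hour entry missing.
- C: 2-hour entry present, rescue between 2 and 3 hours, no pain at 3 hours.

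| Rule | A | B | C |
|---|---|---|---|
| Appendix 4, 3.1, its own sentence read literally | failure | not addressed | not addressed |
| NC=F definition, 2.3 | 3-hour datum present, so not a failure | failure | - |
| RM=F, 2.3, and 5.7.1 | - | - | failure |
| Pain relief at 3 h, Appendix 4, 4.2 | success | failure | failure |
| Sustained pain freedom 3 to 24 h, Appendix 4, 1.1 | success | failure | failure by 5.7.1 |

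Subject A shows the conflict. Section 1.1 needs the 3-hour and 24-hour values, not the 2-hour value, so A has sustained pain freedom starting at 3 hours and yet, by the literal sentence, is not pain free at 3 hours. Both statements cannot be true. Subjects B and C are failures whichever way Section 3.1 is read, because the general rules reach them.

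**Likely origin.** The 2-hour primary analysis (SAP 5.7.3.1) says "Missing data at 2 hours post-dose will be imputed as failures (NC=F". The Appendix 4 sentence differs only in tense, which points to text carried over from the 2-hour analysis.

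**Illustrative size.** Assumptions: 550 per arm; correctly classified 3-hour rates equal to the Phase 2b 2-hour rates; a share m of each arm missing at 2 hours but observed at 3 hours; these subjects respond at their arm's rate. The literal rule then gives a risk difference of (31.4 - 15.3) x (1 - m) points. Responders wrongly failed number 550 x m x 0.314 on rimegepant and 550 x m x 0.153 on placebo.

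| m | Risk difference (points) | Loss from 16.1 | Wrongly failed, rimegepant | Wrongly failed, placebo |
|---|---|---|---|---|
| 1% | 15.9 | 0.2 | 1.7 | 0.8 |
| 3% | 15.6 | 0.5 | 5.2 | 2.5 |
| 5% | 15.3 | 0.8 | 8.6 | 4.2 |
| 10% | 14.5 | 1.6 | 17.3 | 8.4 |

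With unequal shares the loss is 31.4 x m(rimegepant) - 15.3 x m(placebo). The literal rule would enlarge the difference only if the placebo share exceeded 31.4 / 15.3 = 2.05 times the rimegepant share. The documents give no share for either arm.

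**The case against.** The strongest reply is that this is one wrong word beside a correctly defined code. Section 3.1 names NC=F, and Section 2.3 says what that means. A programmer applying the code would use the 3-hour entry, and nothing shows that the literal sentence was programmed. The analysis is post hoc and supportive (SAP Summary of Changes), and with equal missingness the error would shrink the effect. All of that stands, and it limits the size of the point. It does not make the sentence right. Section 3.1 is in the past tense, so it reads as a record of what was done, and a reader cannot tell whether the text or the table is wrong.

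Three stronger readings are tempting, but the documents do not support them.

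- **That subjects rescued between 2 and 3 hours are counted as pain free because Section 3.1 has no rescue sentence.** Rescue is indeed permitted once the 2-hour assessment is complete (Protocol 5.4.1). But SAP 5.7.1 covers any efficacy evaluation at or after rescue, and nothing in Appendix 4 disapplies it. Leaving rescue to the general rules is also common in this SAP: the texts for 2-hour pain freedom (5.7.3.1), pain relief (5.7.4.2) and functional disability (5.7.4.4) have no rescue sentence either.
- **That a missing 3-hour value has no rule.** The NC=F definition already makes it a failure.
- **That the result must disagree with the 3-hour row of Table 14.2.3.8.7.** SAP 5.7.6.5, which describes that tabulation, states no missing-data rule with which Section 3.1 could conflict.

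**Conclusion.** The time point in the missing-data sentence of Appendix 4, Section 3.1 is wrong as written. It contradicts the NC=F definition, the three parallel 3-hour sections that state a rule (3.2, 4.1 and 4.2), and the 3-to-24-hour durability endpoint. The only subjects it can misclassify are those with no 2-hour entry who reported no pain at 3 hours without rescue, and only if the sentence was programmed literally.

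The consequence is minor. It concerns one post-hoc supportive table, outside the fixed sequence in SAP 5.2.5. On the assumptions above, 3-5% of each arm missing at 2 hours but observed at 3 would take about 0.5 to 0.8 points off a 16.1-point difference. Those shares are assumed, and the actual size is unknown. The absence of a rescue sentence in Section 3.1, and of both rules in Section 4.3, is a matter of clarity and misclassifies no one.

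**What to change.** In SAP Appendix 4, Section 3.1, change 2 hours to 3 hours in the missing-data sentence. Confirm how Table 14.2.3.18.1 was programmed. If it used the 3-hour entry, correcting the text is enough; if it used the 2-hour entry, rerun that table and its risk-difference plot. As optional clarity, add a cross-reference to the NC=F definition and to Section 5.7.1 in Appendix 4, Sections 3.1 and 4.3. The cost is one word, one programming check and, at most, a rerun of that single analysis.

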### **3.2 Freedom from MBS at 3 Hours Post Dose**

The estimand, difference in percentage of subjects with freedom from MBS at 3 hours between treatment groups was evaluated by computing the common risk difference using CMH weights (sample size weights), stratified by the use of prophylactic migraine medication (yes or no). The risk difference was tested at a two-sided alpha level of 0.05. Missing data at 3 hours post-dose was imputed as failure (NC=F). Also the use of rescue medication prior to providing data at the 3 hour assessment, taking IP prior to reporting the MBS, or failure to report a MBS are events that were imputed as treatment failures.

Results presented for this analysis included the following:

- Common risk difference with sample size, p-value, ASE, and 95% asymptotic CIs.
- Risk difference within each strata with sample size, p-value, ASE, and 95% asymptotic CIs.
- A plot of the risk differences within each strata, and common risk difference (similar to the risk difference plot produced by SAS Proc Freq).

- Common risk for each treatment with sample size, ASE, and 95% asymptotic CIs.

## **4 OTHER ENDPOINTS AT 3 HOURS POST DOSE**

### **4.1 Freedom from Photophobia, Phonophobia, or Nausea at 3 Hours**

Freedom from photophobia, phonophobia, and nausea were assessed, by treatment group, by tabulating the number of mITT subjects who reported the presence of the symptom at migraine onset, and later reported the absence of the symptom at 3 hours post-dose. Subjects who reported the symptom at baseline, but have missing data at 3 hours post-dose were imputed as failures (NC=F). Also, subjects in the analysis set who took rescue medications on or before providing their 3 hour post-dose data were imputed as failures.

The principal measurement for the associated symptoms (phonophobia, photophobia, and nausea) is made on a binary scale (0 = absent; 1 = present). An exploratory measurement of these symptoms was also made on a 4-point Likert scale (0=none, 1=mild, 2=moderate, 3=severe).

For these three endpoints, the difference between treatment groups, was evaluated by computing the common risk difference using CMH weights (sample size weights), stratified by the use of prophylactic migraine medication (yes or no). The risk difference was tested at a two-sided alpha level of 0.05.

Results presented for these analyses included the following:

- Common risk difference with sample size, p-value, ASE, and 95% asymptotic CIs.
- Risk difference within each strata with sample size, p-value, ASE, and 95% asymptotic CIs.
- A plot of the risk differences within each strata, and common risk difference (similar to the risk difference plot produced by SAS Proc Freq).
- Common risk for each treatment with sample size, ASE, and 95% asymptotic CIs.

### **4.2 Pain Relief at 3 Hours Post Dose**

Pain relief at 3 hours post-dose was assessed by tabulating the number of mITT subjects that reported a pain level of none or mild (responses of 0 or 1 on the 4-point Likert scale) at 3 hours post-dose by treatment group. Subjects with missing data at 3 hours post-dose were imputed as failures (NC=F). Also, subjects in the analysis set who took rescue medications on or before providing their 3 hour post-dose data were imputed as failures.

Results presented for this analysis included the following:

- Common risk difference with sample size, p-value, ASE, and 95% asymptotic CIs.
- Risk difference within each strata with sample size, p-value, ASE, and 95% asymptotic CIs.

- A plot of the risk differences within each strata, and common risk difference (similar to the risk difference plot produced by SAS Proc Freq).
- Common risk for each treatment with sample size, ASE, and 95% asymptotic CIs.

### **4.3 Functional Disability Scale at 3 Hours Post Dose**

Impact of treatment on subject disability was assessed using a single-question, functional disability scale. Subjects rated the level of disability they perceived as a result of their migraine in performing normal actions using a 4-point scale: Normal Function, Mild Impairment, Severe Impairment, or Required Bedrest. The proportion of mITT subjects who had a response of “normal” at 3-hours post dose was evaluated as the endpoint of interest.

Results presented for this analysis included the following:

- Common risk difference with sample size, p-value, ASE, and 95% asymptotic CIs.
- Risk difference within each strata with sample size, p-value, ASE, and 95% asymptotic CIs.
- A plot of the risk differences within each strata, and common risk difference (similar to the risk difference plot produced by SAS Proc Freq).
- Common risk for each treatment with sample size, ASE, and 95% asymptotic CIs.

## **5 ADDITIONAL SAFETY ANALYSES**

### **5.1 Adverse Events Leading to Study Discontinuation**

Adverse events leading to study discontinuation were summarized for the treated subjects by system organ class and preferred term.

### **5.2 Prophylactic Medications**

Prophylactic medications were summarized for the treated subjects by system organ class and preferred term.

### Appendix 5. Tables And Figures For Supportive Analyses

Table Number	Title	Population
14.2.3.7.1.2	Sustained Pain Freedom from 3 to 24 Hours Post Dose: Ad-hoc Analysis	mITT Subjects
14.2.3.7.1.3	Sustained Pain Freedom from 4 to 24 Hours Post Dose: Ad-hoc Analysis	mITT Subjects
14.2.3.7.2.2	Sustained Pain Relief from 3 to 24 Hours Post Dose: Ad-hoc Analysis	mITT Subjects
14.2.3.7.2.3	Sustained Pain Relief from 4 to 24 Hours Post Dose: Ad-hoc Analysis	mITT Subjects
14.2.3.7.3.2	Sustained Pain Freedom from 3 to 48 Hours Post Dose: Ad-hoc Analysis	mITT Subjects
14.2.3.7.3.3	Sustained Pain Freedom from 4 to 48 Hours Post Dose: Ad-hoc Analysis	mITT Subjects
14.2.3.7.4.2	Sustained Pain Relief from 3 to 48 Hours Post Dose: Ad-hoc Analysis	mITT Subjects
14.2.3.7.4.3	Sustained Pain Relief from 4 to 48 Hours Post Dose: Ad-hoc Analysis	mITT Subjects
14.2.3.7.5.1	Sustained MBS Freedom from 2 to 24 Hours Post Dose: Ad-hoc Analysis	mITT Subjects
14.2.3.7.5.2	Sustained MBS Freedom from 3 to 24 Hours Post Dose: Ad-hoc Analysis	mITT Subjects
14.2.3.7.5.3	Sustained MBS Freedom from 4 to 24 Hours Post Dose: Ad-hoc Analysis	mITT Subjects
14.2.3.7.6.1	Sustained MBS Freedom from 2 to 48 Hours Post Dose: Ad-hoc Analysis	mITT Subjects
14.2.3.7.6.2	Sustained MBS Freedom from 3 to 48 Hours Post Dose: Ad-hoc Analysis	mITT Subjects
14.2.3.7.6.3	Sustained MBS Freedom from 4 to 48 Hours Post Dose: Ad-hoc Analysis	mITT Subjects
14.2.3.7.7.1	Sustained Nausea Freedom from 2 to 24 Hours Post Dose: Ad-hoc Analysis	mITT Subjects
14.2.3.7.7.2	Sustained Nausea Freedom from 3 to 24 Hours Post Dose: Ad-hoc Analysis	mITT Subjects
14.2.3.7.7.3	Sustained Nausea Freedom from 4 to 24 Hours Post Dose: Ad-hoc Analysis	mITT Subjects
14.2.3.7.8.1	Sustained Nausea Freedom from 2 to 48 Hours Post Dose: Ad-hoc Analysis	mITT Subjects
14.2.3.7.8.2	Sustained Nausea Freedom from 3 to 48 Hours Post Dose: Ad-hoc Analysis	mITT Subjects
14.2.3.7.8.3	Sustained Nausea Freedom from 4 to 48 Hours Post Dose: Ad-hoc Analysis	mITT Subjects
14.2.3.7.9.1	Sustained Photophobia Freedom from 2 to 24 Hours Post Dose: Ad-hoc Analysis	mITT Subjects
14.2.3.7.9.2	Sustained Photophobia Freedom from 3 to 24 Hours Post Dose: Ad-hoc Analysis	mITT Subjects
14.2.3.7.9.3	Sustained Photophobia Freedom from 4 to 24 Hours Post Dose: Ad-hoc Analysis	mITT Subjects
14.2.3.7.10.1	Sustained Photophobia Freedom from 2 to 48 Hours Post Dose: Ad-hoc Analysis	mITT Subjects
14.2.3.7.10.2	Sustained Photophobia Freedom from 3 to 48 Hours Post Dose: Ad-hoc Analysis	mITT Subjects
14.2.3.7.10.3	Sustained Photophobia Freedom from 4 to 48 Hours Post Dose: Ad-hoc Analysis	mITT Subjects
14.2.3.7.11.1	Sustained Phonophobia Freedom from 2 to 24 Hours Post Dose: Ad-hoc Analysis	mITT Subjects
14.2.3.7.11.2	Sustained Phonophobia Freedom from 3 to 24 Hours Post Dose: Ad-hoc Analysis	mITT Subjects
14.2.3.7.11.3	Sustained Phonophobia Freedom from 4 to 24 Hours Post Dose: Ad-hoc Analysis	mITT Subjects
14.2.3.7.12.1	Sustained Phonophobia Freedom from 2 to 48 Hours Post Dose: Ad-hoc Analysis	mITT Subjects
14.2.3.7.12.2	Sustained Phonophobia Freedom from 3 to 48 Hours Post Dose: Ad-hoc Analysis	mITT Subjects
14.2.3.7.12.3	Sustained Phonophobia Freedom from 4 to 48 Hours Post Dose: Ad-hoc Analysis	mITT Subjects
14.2.3.7.13.1	Sustained Functional Disability Freedom from 2 to 24 Hours Post Dose: Ad-hoc Analysis	mITT Subjects

Table Number	Title	Population
14.2.3.7.13.2	Sustained Functional Disability Freedom from 3 to 24 Hours Post Dose: Ad-hoc Analysis	mITT Subjects
14.2.3.7.13.3	Sustained Functional Disability Freedom from 4 to 24 Hours Post Dose: Ad-hoc Analysis	mITT Subjects
14.2.3.7.13.1	Sustained Functional Disability Freedom from 2 to 48 Hours Post Dose: Ad-hoc Analysis	mITT Subjects
14.2.3.7.13.2	Sustained Functional Disability Freedom from 3 to 48 Hours Post Dose: Ad-hoc Analysis	mITT Subjects
14.2.3.7.13.3	Sustained Functional Disability Freedom from 4 to 48 Hours Post Dose: Ad-hoc Analysis	mITT Subjects
14.2.3.12.1	Kaplan-Meier Time to Rescue Medication up to 24 hours Post Dose: Ad-hoc Analysis	mITT Subjects
14.2.3.12.2	Median Time to Rescue Medication: Ad-hoc Analysis	mITT Subjects
14.2.3.13.1	Kaplan-Meier Time to First Report of Absence of MBS up to 8 hours Post Dose: Ad-hoc Analysis	mITT Subjects
14.2.3.13.2	Median Time to First Report of Absence of MBS: Ad-hoc Analysis	mITT Subjects
14.2.3.13.3	Kaplan-Meier Nominal Time to First Report of Absence of MBS up to 8 hours Post Dose: Ad-hoc Analysis	mITT Subjects
14.2.3.13.4	Median Nominal Time to First Report of Absence of MBS: Ad-hoc Analysis	mITT Subjects
14.2.3.14.1	Kaplan-Meier Time to First Report of Absence of Nausea up to 8 hours Post Dose: Ad-hoc Analysis	mITT Subjects
14.2.3.14.2	Median Time to First Report of Absence of Nausea: Ad-hoc Analysis	mITT Subjects
14.2.3.14.3	Kaplan-Meier Nominal Time to First Report of Absence of Nausea up to 8 hours Post Dose: Ad-hoc Analysis	mITT Subjects
14.2.3.14.4	Median Nominal Time to First Report of Absence of Nausea: Ad-hoc Analysis	mITT Subjects
14.2.3.15.1	Kaplan-Meier Time to First Report of Absence of Photophobia up to 8 hours Post Dose: Ad-hoc Analysis	mITT Subjects
14.2.3.15.2	Median Time to First Report of Absence of Photophobia: Ad-hoc Analysis	mITT Subjects
14.2.3.15.3	Kaplan-Meier Nominal Time to First Report of Absence of Photophobia up to 8 hours Post Dose: Ad-hoc Analysis	mITT Subjects
14.2.3.15.4	Median Nominal Time to First Report of Absence of Photophobia: Ad-hoc Analysis	mITT Subjects
14.2.3.16.1	Kaplan-Meier Time to First Report of Absence of Phonophobia up to 8 hours Post Dose: Ad-hoc Analysis	mITT Subjects
14.2.3.16.2	Median Time to First Report of Absence of Photophonia: Ad-hoc Analysis	mITT Subjects
14.2.3.16.3	Kaplan-Meier Nominal Time to First Report of Absence of Phonophobia up to 8 hours Post Dose: Ad-hoc Analysis	mITT Subjects
14.2.3.16.4	Median Nominal Time to First Report of Absence of Photophonia: Ad-hoc Analysis	mITT Subjects
14.2.3.17.1	Kaplan-Meier Time to First Report of Return to Normal Functioning up to 8 hours Post Dose: Ad-hoc Analysis	mITT Subjects
14.2.3.17.2	Median Time to First Report of Return to Normal Functioning: Ad-hoc Analysis	mITT Subjects
14.2.3.17.3	Kaplan-Meier Nominal Time to First Report of Return to Normal Functioning up to 8 hours Post Dose: Ad-hoc Analysis	mITT Subjects
14.2.3.17.4	Median Nominal Time to First Report of Return to Normal Functioning: Ad-hoc Analysis	mITT Subjects
14.2.3.18.1	Pain Freedom at 3 Hours Post Dose: Ad-hoc Analysis	mITT Subjects
14.2.3.18.2	Freedom from Most Bothersome Symptom at 3 Hours Post Dose: Ad-hoc Analysis	mITT Subjects

Table Number	Title	Population
14.2.3.18.3	Freedom from Photophobia at 3 Hours Post Dose: Ad-hoc Analysis	mITT Subjects
14.2.3.18.4	Freedom from Phonophobia at 3 Hours Post Dose: Ad-hoc Analysis	mITT Subjects
14.2.3.18.5	Pain Relief at 3 Hours Post Dose: Ad-hoc Analysis	mITT Subjects
14.2.3.18.6	Freedom from Nausea at 3 Hours Post Dose: Ad-hoc Analysis	mITT Subjects
14.2.3.18.7	Functional Disability Scale at 3 Hours Post Dose: Ad-hoc Analysis	mITT Subjects
14.3.2.6	Incidence of On-study Adverse Events Leading to Study Discontinuation by System Organ Class and Preferred Term	Treated Subjects
14.5.3.3	Prophylactic Medications by Therapeutic Class and Preferred Term	Treated Subjects

Figure Number	Title	Population
14.2.17	Kaplan Meier Survival Plot of Time to Rescue Medication up to 24 Hours Post Dose	mITT Subjects
14.2.19	Kaplan Meier Survival Plot of Time to First Report of Absence of MBS up to 8 Hours Post Dose	mITT Subjects
14.2.23	Kaplan Meier Survival Plot of Time to First Report of Absence of Nausea up to 8 Hours Post Dose	mITT Subjects
14.2.27	Kaplan Meier Survival Plot of Time to First Report of Absence of Photophobia up to 8 Hours Post Dose	mITT Subjects
14.2.31	Kaplan Meier Survival Plot of Time to First Report of Absence of Phonophobia up to 8 Hours Post Dose	mITT Subjects
14.2.35	Kaplan Meier Survival Plot of Time to First Report of Return to Normal Functioning up to 8 Hours Post Dose	mITT Subjects
14.2.21	Kaplan Meier Survival Plot of Time to First Report of Absence of MBS up to 8 Hours Post Dose (Nominal Time)	mITT Subjects
14.2.25	Kaplan Meier Survival Plot of Time to First Report of Absence of Nausea up to 8 Hours Post Dose (Nominal Time)	mITT Subjects
14.2.29	Kaplan Meier Survival Plot of Time to First Report of Absence of Photophobia up to 8 Hours Post Dose (Nominal Time)	mITT Subjects
14.2.33	Kaplan Meier Survival Plot of Time to First Report of Absence of Phonophobia up to 8 Hours Post Dose (Nominal Time)	mITT Subjects
14.2.37	Kaplan Meier Survival Plot of Time to First Report of Return to Normal Functioning up to 8 Hours Post Dose (Nominal Time)	mITT Subjects

